9.4 Assessments

1) Assessments

Pregnancy during the observation period (females only)

2) Outcome measure data collection timing

Period from the start of Leuplin PRO treatment to 24 weeks after the start of treatment (or discontinuation of observation)

9.5 Adverse Events (AEs)

1) Surveillance items

Presence or absence of injection site reaction, details of injection site reaction (specific symptom, date of onset, seriousness and reason for seriousness [refer to Table 2], cause of discontinuation of Leuplin PRO treatment, intervention (presence or absence and contents), date of outcome assessment, outcome, causal relationship to Leuplin PRO [refer to Table 3]).

Presence or absence of AE other than injection site reaction (refer to Table 1), AE term, date of onset, seriousness and reason for seriousness (refer to Table 2), cause of discontinuation of Leuplin PRO treatment, intervention (presence or absence and name of the drug/intervention), date of outcome assessment, outcome, causal relationship to Leuplin PRO* (refer to Table 3)

Patients with “not resolved” or “unknown” outcome or “unevaluable” causal relationship should be followed up wherever possible.

* For the causal relationship to Leuplin PRO, the rationale for “not related” and the reason for “unevaluable” shall be collected.

Note) Additional points to consider for AEs

Abnormal worsening of target disease, for instance, worsening beyond the expected natural course of the disease, will be handled as an AE.

- 2) Time points of surveillance
Period from the start of Leuplin PRO treatment to 24 weeks after the start of treatment (or discontinuation of observation)

Table 1 Definition of adverse events

An AE is defined as any untoward medical occurrence in a clinical investigation subject administered a drug; it does not necessarily have to have a causal relationship with this treatment. An AE can therefore be any unfavorable or unintended sign (e.g., abnormal laboratory finding), symptom, or disease temporally associated with the use of a drug, whether or not it is considered related to the drug.

The following are also handled as AEs:

- Symptoms and so forth that occur in infants breast-fed by their mothers under treatment with a drug
- Untoward symptoms and so forth that occur in children treated with a drug
- Symptoms and so forth that occur as a result of occupational exposure to a drug
- Symptoms and so forth that occur after administration of counterfeit medicines of our ethical drugs
- Untoward symptoms that have become known to occur in drug users through lawsuits or other legal actions

Table 2 Criteria for assessing seriousness

An AE satisfying any of the following is assessed as serious:

1. Results in death (death)
2. Is life-threatening (risk of death)
3. Requires inpatient hospitalization or prolongation of existing hospitalization (hospitalization/prolonged hospitalization)
4. Results in persistent or significant disability/incapacity (disability)
5. Leads to a congenital anomaly/birth defect (congenital anomaly)
6. Is an important medical event according to 1 to 5 described above, including AEs in Takeda Medically Significant AE List

Takeda Medically Significant AE List

- Acute respiratory failure / acute respiratory distress syndrome (ARDS)
- Anaphylactic shock
- Torsade de pointes / ventricular fibrillation / ventricular tachycardia
- Acute renal failure
- Malignant hypertension
- Pulmonary hypertension
- Convulsive seizures (including convulsions and epilepsy)
- Pulmonary fibrosis (including interstitial pneumonia)
- Agranulocytosis
- Malignant syndrome / malignant hyperthermia

- Aplastic anemia
- Spontaneous abortion / stillbirth and fetal death
- Toxic epidermal necrolysis / mucocutaneous ocular syndrome (Stevens-Johnson syndrome)
- Confirmed or suspected transmission of infectious agent by a medicinal product
- Hepatic necrosis
- Confirmed or suspected endotoxin shock
- Acute liver failure

Table 3 Criteria for assessing the relationship of each adverse event to Leuplin PRO

| Assessment | Criteria for assessment |
|-------------|---|
| Related | An AE that follows a reasonable temporal sequence from administration of a drug (including the course after withdrawal of the drug), or for which possible involvement of the drug can be argued, although factors other than the drug, such as underlying diseases, concurrent illnesses, concomitant drugs, and concomitant treatments, may also be responsible |
| Not related | An AE that does not follow a reasonable temporal sequence from administration of a drug and/or that can reasonably be explained by other factors, such as underlying diseases, concurrent illnesses, concomitant drugs, and concomitant treatments |
| Unevaluable | Information necessary for evaluation, including temporal sequence from administration of a drug (including the course after withdrawal of the drug), underlying diseases, concurrent illnesses, concomitant drugs, and concomitant treatments, is not sufficient. |

10.0 Analysis Items and Methods

10.1 Statistical Analysis Plan

A statistical analysis plan will be prepared before finalization of data. The statistical analysis plan will include definitions of endpoints and detailed analysis methods.

10.2 Analysis Sets

The analysis set is patients included in safety evaluation.

10.3 Matters on Patient Composition

The number of enrolled patients, number of patients with the (electronic) CRF collected, number of patients included in safety evaluation, number of patients excluded from safety evaluation, and reason for exclusion will be tabulated.

10.4 Patient Baseline Characteristics

Patient baseline characteristics, including age, predisposition to hypersensitivity, and concurrent illness, will be tabulated.

10.5 Treatment Given

The treatment status of Leuplin PRO and treatment status of premenopausal breast cancer drug other than Leuplin PRO will be tabulated.

10.6 Matters on Safety

For patients included in safety evaluation, data will be tabulated as described below. AEs will be coded according to the MedDRA/J and summarized using preferred term (PT) and system organ class (SOC).

10.6.1 Occurrence of Adverse Events

For AEs reported during the observation period, the incidence will be tabulated by type, time of onset, seriousness, and causal relationship to Leuplin PRO. In addition, events listed as the safety specifications for the surveillance in “2. Summary of Pharmacovigilance Plan” in the risk management plan will be tabulated separately.

10.6.2 Factors that May Affect the Safety

For ADRs reported during the observation period, the incidence will be tabulated by patient background factors (e.g., disease status, presence or absence of concurrent renal impairment, presence or absence of concurrent hepatic impairment) and treatment status of Leuplin PRO.

11.0 Posting of Surveillance Information

Surveillance information will be posted on the following open website before starting the surveillance:

- Japan Pharmaceutical Information Center-Clinical Trials Information

14.0 Other Necessary Matters

14.1 Revision of the Protocol

During the surveillance, attention will be paid to comprehend the status of progression of the surveillance, presence or absence of ADRs that are unexpected based on the precautions/serious ADRs, presence or absence of increased incidence of certain ADRs, and appropriateness of surveillance items, and this protocol will be reviewed and revised if necessary. If partial change to dosage and administration or indications is approved during the surveillance, the necessity of revising the protocol will be discussed if necessary, and the protocol will be revised as needed.

14.2 Actions to be Taken for Problems and Questions

If any safety problem is detected, data will be carefully examined to discuss measures.

Appendix Observation schedule

| Time point of surveillance | | Observation period | | |
|----------------------------------|--|-------------------------|---------------------------|---|
| | | At patient registration | At the start of treatment | After 24 weeks or at discontinuation of observation |
| Surveillance item | | | | |
| Patient registration | Date of administration of Leuplin PRO | ○ | | |
| | Patient identification number | ○ | | |
| | Patient initials | ○ | | |
| | Date of birth | ○ | | |
| | Assessment based on the exclusion criteria | ○ | | |
| Patient baseline characteristics | Time of diagnosis of premenopausal breast cancer | | ○ | |
| | ECOG Performance Status | | ○ | |
| | Disease status | | ○ | |
| | Diagnostic category | | ○ | |
| | Site of lesions before the start of Leuplin PRO treatment | | ○ | |
| | Presence or absence of hormone receptor expression | | ○ | |
| | Predisposition to hypersensitivity | | ○ | |
| | Concurrent illness | | ○ | |
| | History of thromboembolism | | ○ | |
| | Height, body weight | | ○ | |
| | Treatment status of premenopausal breast cancer drug immediately before the start of Leuplin PRO treatment | | ○ | |
| Treatment given | Treatment status of Leuplin PRO | | ← ○ → | |
| | Treatment status of premenopausal breast cancer drug other than Leuplin PRO | | ← ○ → | |
| Assess-ments | Pregnancy during the observation period (females only) | | ← ○ → | |
| Adverse event | Injection site reaction | | ← ○ → | |
| | Adverse event other than injection site reaction | | ← ○ → | |

○ : Performed

← ○ → : Performed throughout the period

1.1 List of Terms and Abbreviations

- Leuplin PRO: Leuplin PRO for Injection Kit 22.5 mg is abbreviated as Leuplin PRO.
- Adverse drug reaction (ADR), etc.: ADR, etc. is an abbreviation of ADR/infection. ADRs, etc. refer to all adverse events (AEs) other than those assessed by the investigator to be not related to Leuplin PRO. In this document, “adverse drug reactions/infections” is used in titles, and “ADR, etc.” is used in the text and tables.
- Serious adverse event (SAE): A SAE is an adverse event assessed by the investigator to be serious. Events included in the MedDRA code list in Takeda Medically Significant AE List will be handled as serious even if assessed by the investigator to be not serious.
- Causal relationship: An event assessed as not related to Leuplin PRO will be handled as “not related.” Events not unrelated to Leuplin PRO in the text and tables refer to all events other than those assessed as not related to Leuplin PRO.
- Summary statistics: Collective term for number of patients, mean, standard deviation, maximum, minimum, and quartiles
- Patient with no CRF collected: Enrolled patient for whom the CRF has not been collected
- Patient with the CRF collected: Enrolled patient for whom the CRF has been collected
- Finalized patient: Patient for whom the CRF has been collected and finalized at least once by data lock point
- Non-finalized patient: Patient for whom the CRF has been collected, but has not been finalized by data lock point
- Age: If the month and day of starting Leuplin PRO treatment is smaller than the month and day of birth, age will be calculated as year of starting Leuplin PRO treatment - year of birth - 1. If the month and day of starting Leuplin PRO treatment is equal to or greater than the month and day of birth, age will be calculated as year of starting Leuplin PRO treatment - year of birth. If the day of birth is unknown, 1 will be used for calculation.
- Time from diagnosis of premenopausal breast cancer to patient registration (months):
 - Actual number (units: month) = (“date of patient registration” - “date of diagnosis” + 1)/30.44
- BMI (kg/m²): Calculated as body weight (kg)/height (m)² (displayed to one decimal place by rounding)

- Induration: AE with “induration” selected for “Specific symptom (multiple answers allowed)” in the column of [Adverse event: Injection site reaction] in the CRF

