9.5 Adverse Events (AEs)

1) Surveillance items

Presence or absence of injection site reaction, details of injection site reaction (specific symptom, date of onset, seriousness and reason for seriousness [refer to Table 2]), cause of discontinuation of Leuplin PRO treatment, intervention (presence or absence and contents), date of outcome assessment, outcome, causal relationship to Leuplin PRO [refer to Table 3]).

Presence or absence of AE other than injection site reaction (refer to Table 1), AE term, date of onset, seriousness and reason for seriousness (refer to Table

2), cause of discontinuation of Leuplin PRO treatment, intervention (presence or absence and name of the drug/intervention), date of outcome assessment, outcome, causal relationship to Leuplin PRO* (refer to Table 3)

Patients with “not resolved” or “unknown” outcome or “unevaluable” causal relationship should be followed up wherever possible.

* For the causal relationship to Leuplin PRO, the rationale for “not related” and the reason for “unevaluable” shall be collected.

Note) Additional points to consider for AEs

Abnormal worsening of target disease, for instance, worsening beyond the expected natural course of the disease, will be handled as an AE.

2) Time points of surveillance

Period from the start of Leuplin PRO treatment to 24 weeks after the start of treatment (or discontinuation of observation)

Table 1 Definition of adverse events

An AE is defined as any untoward medical occurrence in a clinical investigation subject administered a drug; it does not necessarily have to have a causal relationship with this treatment. An AE can therefore be any unfavorable or unintended sign (e.g., abnormal laboratory finding), symptom, or disease temporally associated with the use of a drug, whether or not it is considered related to the drug.

The following are also handled as AEs:

- Symptoms and so forth that occur in infants breast-fed by their mothers under treatment with a drug
- Untoward symptoms and so forth that occur in children treated with a drug
- Symptoms and so forth that occur as a result of occupational exposure to a drug
- Symptoms and so forth that occur after administration of counterfeit medicines of our ethical drugs
- Untoward symptoms that have become known to occur in drug users through lawsuits or other legal actions

Table 2 Criteria for assessing seriousness

An AE satisfying any of the following is assessed as serious:

1. Results in death (death)

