5.3 Occurrence of Injection Site Reaction Not Unrelated to Leuplin PRO

5.3.1 Occurrence of Injection Site Reaction Not Unrelated to Leuplin PRO

Patients included Safety population

in analysis:

Analysis item: Injection site reaction not unrelated to Leuplin PRO

Stratification factors: Specific symptom (multiple answers allowed) [Pain, pruritus, erythema, swelling, induration, abscess, ulcer, other]

Analysis methods: For the aforementioned analysis item, frequency tabulation will be performed in each stratum of the stratification factor.

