5.3.2 Detail of Induration Not Unrelated to Leuplin PRO

Patients included Patients in the safety population who experienced induration not unrelated to
in analysis: Leuplin PRO

Analysis items:	Seriousness	[Serious, not serious]
	Abscess/ulcer	[No, yes]
	Size of induration (longest diameter)	[-10 mm, 11-20 mm, 21-30 mm, 31-40 mm, 41 mm-, unknown]
	Number of days from Leuplin PRO treatment to the day of onset	[<7 days, 7-<28 days, 28-<56 days, 56-<84 days, 84-<168 days, >=168 days]
	Cause of discontinuation of Leuplin PRO treatment	[Yes, no]
	Presence or absence of intervention	[No, yes]
	Outcome	[Recovered, recovering, not recovered, recovered with sequelae, died, unknown, unknown]
	Number of days from the day of onset to “recovered” or “recovering” (frequency tabulation with only patients who recovered or were recovering as the denominator)	[<7 days, 7-<28 days, 28-<56 days, 56-<84 days, 84-<168 days, >=168 days]

Analysis methods: For the aforementioned analysis items, frequency tabulation will be performed for discrete data, and summary statistics will be calculated for continuous data.

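### On records with several symptoms ticked, the onset, seriousness, outcome and recovery time that SAP 5.3.2 reports for induration may belong to another symptom

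*SAP*

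**What the plan says.** SAP 1.1 defines induration at the level of the AE record, as an "AE with “induration” selected for “Specific symptom (multiple answers allowed", in the CRF column for injection site reactions. SAP 5.3.1 shows the answers available for that symptom field: "Pain, pruritus, erythema, swelling, induration, abscess, ulcer, other".

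Protocol 9.5 sets out what is collected when an injection site reaction occurs: "details of injection site reaction (specific symptom, date of onset, seriousness and reason for seriousness", then whether it led to discontinuation, then "intervention (presence or absence and contents), date of outcome assessment, outcome, causal relationship to Leuplin PRO [refer to Table 3". Symptom is one item in this list. No date, seriousness or outcome for each symptom is described.

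SAP 5.3.2 takes "Patients in the safety population who experienced induration not unrelated to" Leuplin PRO. It tabulates seriousness, "Number of days from Leuplin PRO treatment to the day of onset", intervention, outcome, and the time from onset until recovered or recovering. It also has a yes/no item "Abscess/ulcer" and the longest diameter of the induration. It does not say how a record with other symptoms ticked is handled, and it has no restriction to, or split by, records with induration alone.

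**The concern.** The table is headed as detail of induration, but most of its rows describe a record. Suppose a patient has pain on the day of injection and a lump three weeks later, and the site enters both as one reaction. The record has both symptoms ticked. If its onset date is that of the pain, the table shows an induration in the first week. If an abscess on the same record made it serious, the table shows a serious induration.

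This matters because protocol 3.2 names time of onset and seriousness, with incidence, as what the surveillance is to examine for injection site reactions and other ADRs. Induration is the only specific symptom with its own detail table (SAP 5.3.2) and factor table (SAP 5.3.3). Its onset and recovery rows are likely to be read as showing how lumps develop after the larger single dose and the changed release profile. On mixed records they may not show that.

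**Working it through.** **The plan's own figure.** The documents contain one calculated quantity, the sample size in protocol 3.2. The probability of seeing at least one case of a 1% ADR in 300 patients is 1 − 0.99^300 = 0.9510, and the smallest n reaching 0.95 is 299. The 300 reproduces. The present point does not depend on it.

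**Tracing each row of SAP 5.3.2 to its source**

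1. *Who enters the table.* Patients with a related record on which induration is ticked (SAP 1.1). Other ticks neither add nor remove anyone.
2. *What the attributes are attached to.* In protocol 9.5, onset, seriousness, intervention and outcome are details of the injection site reaction, and symptom is a further detail of the same reaction.
3. *Combining 1 and 2.* If induration is the only tick, the reaction's attributes are those of induration. If two or more symptoms are ticked, the attributes belong to the record, and the documents do not say which symptom sets them.
4. *Whether an existing row separates them.* The abscess/ulcer item is a one-way frequency, not crossed with seriousness, onset or outcome. A reader who sees one serious case and one abscess cannot tell whether they are the same case. Pain, pruritus, erythema and swelling do not appear in 5.3.2. SAP 5.3.1 counts each symptom without showing which occurred together.
5. *What is untouched.* Counts in 5.3.1 and incidence in 5.3.3 need only the induration tick. Longest diameter is specific to induration.

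**Whether a shared date can change a row.** SAP 1.5 computes onset as event date − treatment date + 1. Pain on the injection day is day 1, in the band below 7 days. A lump 21 days later is day 22, in the 7 to <28 day band. One date for both puts the record in the wrong band for one of the two symptoms. If both symptoms start in the same band, nothing changes.

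**Size.** The documents give no induration rate and no share of mixed records. As an illustration only, assume all 300 patients are evaluable, one record per affected patient, an induration rate r of 1% to 20%, and a share m of records with another symptom ticked of 20% to 80%. Then mixed records = 300 × r × m.

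| r | Records, 300 × r | m = 20% | m = 50% | m = 80% |
|---|---|---|---|---|
| 1% | 3 | 0.6 | 1.5 | 2.4 |
| 5% | 15 | 3 | 7.5 | 12 |
| 10% | 30 | 6 | 15 | 24 |
| 20% | 60 | 12 | 30 | 48 |

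These are records whose attributes could not be assigned to induration alone, not records that are wrong. If sites made one entry per symptom, m is 0 and so is every cell.

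**The case against.** The strongest objection is that the CRF is not in the documents. Protocol 9.5 never says that a reaction has only one onset date, and it is not a full list of CRF fields: SAP 5.3.2 tabulates induration size, which 9.5 does not mention. Nothing stops a site from entering early pain and a later lump as two reactions. This stands. It limits the point to what *may* happen. It does not remove it, because a multiple-answer field invites mixed records and the SAP has no rule for them.

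Second, abscess/ulcer in 5.3.2 may refer to the same record or to another record in the same patient, so it does not prove that mixed records are expected. That stands too. If it does mean the same record, part of the overlap is already disclosed, though not linked to seriousness.

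Third, 5.3.2 is not the only source. SAP 5.2.2 tabulates ADRs by PT with seriousness, onset and outcome, and SAP 5.1.5 tabulates the injection site reaction risk by PT and seriousness. Protocol 3.2 asks about injection site reactions, for which record-level onset is a fair answer. All true, but the SAP does not say whether a record with several symptoms is coded to one PT or several, so those tables do not clearly resolve the question for induration.

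Fourth, resting every statement on induration-only records would drop cases with abscess or ulcer and could understate seriousness. This is right, and it shapes the fix.

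**Conclusion.** The point holds as a limit on interpretation. The onset, seriousness, intervention, outcome and recovery time in SAP 5.3.2 are those of injection site reactions that included induration, and on mixed records they may belong to another symptom. How often this happens cannot be derived; the illustration runs from 0 to 48 records and rests wholly on assumed rates.

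A reader might infer three stronger things, none of which the documents support:

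- *Onset of induration is biased early.* That needs the record to carry the first symptom's date and the symptoms to fall in different bands. Neither is stated.
- *Seriousness of induration is overstated, or its duration lengthened.* Either is possible on a given record; no rule or data show it in general.
- *The induration results as a whole are unreliable.* Counts, incidence and size do not depend on the shared attributes, and induration-only records are unaffected.

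**What to change.** In SAP 5.3.2, for seriousness, days to onset, intervention, outcome and days to recovery:

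- keep the column for all induration records, labelled *injection site reactions that included induration*;
- add two columns, *induration the only symptom selected* and *induration with other symptoms*;
- cross abscess/ulcer with seriousness.

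Read onset and recovery time for induration itself from the induration-only column, with the all-records column beside it. Report seriousness for all records, so that cases with abscess or ulcer stay in view.

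The split uses symptom ticks already tabulated in SAP 5.3.1, so no new data are needed. The cost is smaller cells in a descriptive table and an induration-only group that may be milder than the whole. If there are no mixed records, the split will show that.

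Collecting a date and outcome for each symptom under protocol 9.5 is not proposed for this surveillance. The SAP is dated 4 April 2019. The latest registration date in protocol 8.0 is 28 February 2018, and 24 weeks (168 days) from then ends on 15 August 2018, so the change would come too late.
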